6.1. General Considerations

The Schedule of Assessments is provided in Appendix E for the vaccination period and the follow-up period, and Appendix F for the extension period.

Continuous variables will be summarized using the following descriptive summary statistics: the number of subjects (n), mean, standard deviation (SD), median, minimum (min), and maximum (max).

Categorical variables will be summarized using counts and percentages.

Baseline value, unless specified otherwise, is defined as the most recent non-missing measurement (scheduled or unscheduled) collected before the first dose of IP. For immunogenicity tests, the baseline is defined as the most recent non-missing measurement (scheduled or unscheduled) collected before or on the date of first dose of IP.

For the summary statistics of all numerical variables unless otherwise specified, the display precision will follow programming standards. Please see Appendix A for variable display standards.

When count data are presented, the percentage will be suppressed when the count is zero in order to draw attention to the non-zero counts. A row denoted "Missing" will be included in count tabulations where specified on the shells to account for dropouts and missing values. The denominator for all percentages will be the number of subjects in that vaccination group within the analysis set of interest, unless otherwise specified.

Study day relative to the first injection will be calculated as below:

a) study day prior to the first injection will be calculated as: date of assessment/event
 date of the first injection;

b) study day on or after the date of the first injection will be calculated as: date of assessment/event – date of the first injection + 1;

Study day relative to the most recent injection will be calculated as below:

- a) study day prior to the first injection will be calculated as: date of assessment/event
 date of the first injection;
- b) study day on or after the date of the first injection but before the second injection (if applicable) will be calculated as: date of assessment/event date of the first injection + 1;
- c) study day on or after the date of the second injection will be calculated as: date of assessment/event – date of the second injection + 1; if study day is on the same day as the second injection, date and time will be compared with the second injection date and time.

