For calculation regarding antibody titers/antibody concentrations, antibody values reported as below LLOQ will be replaced by 0.5 × LLOQ. Values that are greater than the upper limit of quantification (ULOQ) will be converted to the ULOQ. Missing results will not be imputed.

The following stages for safety analyses will be used in this study:

- Up to 28 days after any vaccination: this stage starts at the day of each vaccination
 and continue through the earliest date of (the day of each vaccination and 27
 subsequent days, next vaccination [if applicable]). This analysis period will be used
 as the primary analysis period for safety analyses including unsolicited AE, except
 for solicited AR, unless specified otherwise.
- Up to 28 days after the first vaccination.
- Up to 28 days after the second vaccination.
- Overall stage: this analysis period starts at the first injection on Day 1 and continues through the earliest date of (study completion, discontinuation from the study, or death).

Unscheduled visits: Unscheduled visit measurements will be included in analysis as follows:

- In scheduled visit windows per specified visit windowing rules.
- In the derivation of baseline/last on-treatment measurements.
- In the derivation of maximum/minimum on-treatment values and maximum/minimum change from baseline values for safety analyses.
- In individual subject data listings as appropriate.

Visit windowing rules: The analysis visit windows for protocol-defined visits are provided in Appendix B.

Incomplete/missing data:

- Imputation rules for missing prior/concomitant medications, non-study vaccinations and procedures are provided in Appendix C.
- Imputation rules for missing AE dates are provided in Appendix D.
- For laboratory assessments, if majority of results are indefinite, imputation of these values will be considered. If the laboratory results are reported as below the LLOQ (e.g., <0.1), the numeric values will be imputed by 0.5 × LLOQ in the summary. If the laboratory results are reported as greater than the ULOQ (e.g., >3000), the numeric values will be imputed by ULOQ in the summary.
- Other incomplete/missing data will not be imputed, unless specified otherwise.

Treatment groups:

The following vaccination groups will be used for summary purposes:

- mRNA-1893 vaccine: μg (2-dose)
- mRNA-1893 vaccine: CCI μg (2-dose)
- mRNA-1893 vaccine: μg (single-dose)
- mRNA-1893 vaccine: Total
- Placebo

Summary by flavivirus serostatus:

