6.2.4. Prior and Concomitant Medications

Prior and concomitant medications and non-study vaccination will be coded using the World Health Organization (WHO) drug dictionary (WHODD). The summary of concomitant medications will be based on the Safety Set. Categorization of prior, concomitant, and post medications is summarized in Appendix C Table 4.

The number and percentage of subjects using concomitant medications and non-study vaccination during the 7-day follow-up period (i.e., on the day of injection and the 6

subsequent days) and during the 28 day follow-up period after each injection (i.e., on the day of injection and the 27 subsequent days) will be summarized by flavivirus serostatus and vaccination group as defined in Section 6.1 as follows:

- Any concomitant medications and non-study vaccination within 7 Days Post Injection
- Any concomitant medications and non-study vaccination within 28 Days Post Injection
- Antipyretic or analgesic medication within 28 Days Post Injection

A summary table of concomitant medications and non-study vaccination that continued or newly received at or after the first injection through 28 days after the last injection will be provided by PT in descending frequency in the mRNA-1893 group with all dose level combined.

Medications taken to prevent pain or fever will be collected on eDiary and summaries will be provided based on the Solicited Safety Set by flavivirus serostatus and vaccination group as defined in Section 6.1 for each injection (first or second) and any injection, including within 7 days after injection.

Prior, concomitant and post medications and non-study vaccination will be presented in a listing.

Concomitant Procedures will be presented in a listing.

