6.3.1. Adverse Events

An AE is defined as any untoward medical occurrence in a subject or clinical investigation subject who is administered a pharmaceutical product at any dose that does not necessarily have to have a causal relationship with the treatment.

A treatment-emergent AE (TEAE) is defined as any event occurring during the study not before exposure to study vaccine or any event already present that worsens after exposure to study vaccine. Adverse events will also be evaluated by the investigator for the coexistence of MAAE which is defined as an AE that leads to an unscheduled visit to a healthcare practitioner.

Unsolicited AEs will be coded by PT and SOC using MedDRA summarized by baseline flavivirus serostatus, vaccination group, and stage (up to 28 days after each vaccination, up to 28 days after any vaccination and overall stage; see Section 6.1 for definitions of vaccination group and stage).

All summary tables (except for the overall summary of AEs) for unsolicited AEs will be presented by SOC and PT for TEAEs with counts of subjects included. SOC will be displayed in internationally agreed order. PT will be displayed in descending order of frequency of total mRNA-1893 and then alphabetically within SOC. When summarizing the number and percentage of subjects with an event, subjects with multiple occurrences of the same AE or a continuing AE will be counted once. Subjects will be presented according to the highest severity (the strongest relationship) in the summaries by severity (of related AEs), if subjects reported multiple events under the same SOC and/or PT.

Percentages will be based upon the number of subjects in the Safety Set within each vaccination group.

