6.3.1.5. Solicited Adverse Reactions

All summary tables for solicited ARs will be provided by baseline flavivirus serostatus (flavivirus-seropositive, flavivirus-seronegative, and/or overall).

An AR is any AE for which there is a reasonable possibility that the test product caused the AE. The term "Solicited Adverse Reactions" refers to selected signs and symptoms occurring after injection administration during a specified post-injection follow-up period (day of injection and 6 subsequent days). The solicited ARs are recorded by the subject in eDiary. The occurrence and intensity of selected signs and symptoms is actively solicited from the participant during a specified post-injection follow-up period (day of injection and 6 subsequent days), using a pre-defined checklist in the eDiary (i.e., solicited ARs).

The following local ARs will be solicited: pain at injection site, erythema (redness) at injection site, swelling (hardness) at injection site.

The following systemic ARs will be solicited: headache, fatigue, myalgia (muscle aches all over the body), arthralgia (aching in several joints), nausea/vomiting, fever, and chills.

The solicited ARs will be graded based on the grading scales presented in Table 13 in the protocol, modified from the Toxicity Grading Scale for Healthy Adult and Adolescent Volunteers Enrolled in Preventative Vaccine Clinical Trials (DHHS 2007). Investigator will assess Grade 4 events (with exception of fever).

If a solicited local or systemic AR continues beyond 7 days post injection, the participant will be prompted to capture solicited local or systemic AR in the eDiary until resolution.

All solicited ARs (local and systemic) will be considered causally related to vaccination.

All solicited ARs analyses will be based on Solicited Safety Set. All solicited ARs analyses will be provided by flavivirus serostatus and vaccination group as defined in Section 6.1 for each vaccination (first, second), unless otherwise specified.

The number and percentage of subjects who reported any solicited AR, any solicited local AR, and any systemic solicited AR during the 7-day follow-up period after each vaccination will be tabulated by flavivirus serostatus, vaccination group, and vaccination,

with a two-sided 95% exact CI using the Clopper-Pearson method. The same analysis will be conducted for subgroups defined by region (United States and Puerto Rico).

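### The mRNA-1893 Total column has no per-injection rule, so as written its first-injection safety tables pool Arm C, which received saline on Day 1

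*SAP*

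**What the plan says.** SAP 6.1 lists five summary groups: the two 2-dose groups, the single-dose group, "mRNA-1893 vaccine: Total" and Placebo. It gives no definition of Total. The nearest wording is in SAP 6.2.4, which speaks of combining all dose levels and makes no distinction by injection.

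SAP 5.3 sets the as-treated group once per participant, for both the Solicited Safety Set and the Safety Set. Someone given placebo first and mRNA-1893 second belongs to mRNA-1893 Single Dose. By SAP 4.1 and its Table 1, that is the planned sequence for Arm C.

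These groups are crossed with injection in three places:

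- Solicited reactions (SAP 6.3.1.5): "vaccination group as defined in Section 6.1 for each vaccination (first, second), unless otherwise specified".
- Unsolicited adverse events (SAP 6.3.1), by stage, where SAP 6.1 includes the stage "Up to 28 days after the first vaccination".
- eDiary medication for pain or fever (SAP 6.2.4): "vaccination group as defined in Section 6.1 for each injection (first or second) and any injection".

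On denominators, SAP 6.1 says "The denominator for all percentages will be the number of subjects in that vaccination group within the analysis set of interest", with an allowance for exceptions specified elsewhere. SAP 6.3.1 says "Percentages will be based upon the number of subjects in the Safety Set within each vaccination group".

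**The concern.** Followed literally, these rules produce a first-injection column headed mRNA-1893 in which a third of the people had received saline. Solicited reactions and unsolicited events after each injection are primary safety endpoints. SAP 6.3.1.5 also treats every solicited reaction as causally related to vaccination, so Arm C's Day 1 saline reactions would be reported as related within an mRNA-1893 total. Total sets the order of preferred terms as well (SAP 6.3.1 and 6.3.1.3). Pooling pulls the contrast with Placebo towards no difference, which is the less cautious direction for safety.

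**Working it through.** **The plan's own figures.** SAP Table 2 gives the lowest event rate detectable with 95% probability. The formula 1 − 0.05^(1/n) returns 2.951%, 1.487%, 0.746% and 0.498% for n = 100, 200, 400 and 600, which matches the printed 2.95, 1.49, 0.75 and 0.5. The plan states no figure for the Total column itself.

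**Who is in the column.** SAP 4.3 plans 200 participants per arm. The three mRNA-1893 groups sum to 600. Only Arms A and B (400) receive mRNA-1893 on Day 1, so 200/600 = 33% of a first-injection Total are saline recipients.

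**Effect on the difference from Placebo.** Let a and b be the first-injection rates in Arms A and B, and p0 the rate after saline. By randomization p0 has the same expectation in Arms C and D.

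- A+B rate = (a + b)/2
- Total rate = (a + b + p0)/3
- Total − p0 = (a + b − 2·p0)/3 = (2/3) × [(a + b)/2 − p0]

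The factor of two thirds does not depend on p0. With unequal arms, and A+B pooled by size, it becomes the share of Total that received mRNA-1893 at that injection.

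**Effect on the crude rate.** Total exceeds A+B whenever p0 exceeds (a + b)/2, so the direction depends on a saline rate that the documents do not give. For illustration I use the Phase 1 first-dose rates at the two dose levels (Protocol 2.3.2): headache and fatigue each 21.7% and 12.5%, myalgia 13% and 4.2%, nausea 8.7% and 12.5%. The saline rate is assumed to be 0, 5 or 10%.

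| Reaction | Assumed p0 | A+B | Total | A+B − p0 | Total − p0 |
|---|---|---|---|---|---|
| Headache or fatigue | 0% | 17.1% | 11.4% | 17.1 | 11.4 |
| | 5% | 17.1% | 13.1% | 12.1 | 8.1 |
| | 10% | 17.1% | 14.7% | 7.1 | 4.7 |
| Nausea | 0% | 10.6% | 7.1% | 10.6 | 7.1 |
| | 5% | 10.6% | 8.7% | 5.6 | 3.7 |
| | 10% | 10.6% | 10.4% | 0.6 | 0.4 |
| Myalgia | 0% | 8.6% | 5.7% | 8.6 | 5.7 |
| | 5% | 8.6% | 7.4% | 3.6 | 2.4 |
| | 10% | 8.6% | 9.1% | −1.4 | −0.9 |

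In the last row pooling raises the crude rate. The Phase 1 percentages imply only about 23 to 24 people per dose level (5/23 = 21.7%, 3/24 = 12.5%), so the absolute values are rough. Only the two-thirds relation is firm.

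**Rare events.** At a true first-dose rate of 0.5%, the chance of at least one event is 1 − 0.995^400 = 86.5% among the 400 exposed on Day 1. A column of 600 would suggest 1 − 0.995^600 = 95.1%.

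**The case against.** The strongest reply is that Total is a supplementary column. The protocol's list of treatment arms has four entries and no Total, and the primary safety objective compares the regimens with placebo. Arms A and B appear undiluted beside Arm C, so a reader can pool them. No hypothesis is tested. SAP 6.1 uses the period up to 28 days after any vaccination "as the primary analysis period for safety analyses including unsolicited AE", and there a denominator of about 600 is right. All of this stands and limits the weight of the point.

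A second reply is that pooling by regimen is coherent: one group per participant, with Total as the sum of the columns beside it. That is a defensible display, but then the heading misdescribes the column for Day 1 and nothing in the SAP warns the reader.

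Third, the table shells may hold a rule, and the SAP allows exceptions. A reader might infer that the SAP expressly places Arm C's saline injection in Total. It does not. Pooling is what the visible text yields when its rules are combined.

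Three further inferences go too far:

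- *That Total always understates first-injection reaction rates.* The myalgia row at an assumed 10% shows otherwise.
- *That first vaccination has no settled meaning.* SAP Table 1 does label Arm C's Day 29 injection as its first vaccination. But SAP 6.1 counts study days from the first and second injection, SAP 6.2.4 refers to the first or second injection, and SAP 6.3.1.5 numbers doses 1 and 2. Injection order is the better reading, and one sentence would confirm it.
- *That the SAP 5.3 rule for a single placebo injection materially distorts exposure.* Arm C participants who stop before Day 29 do sit under Single Dose, but the disposition tables (SAP 6.2.1) and the administration listing (SAP 6.2.5) already show who received each dose. If 2 to 10% of Arm C missed Day 29 (an assumption), 4 to 20 people would be involved. The detectable rate at n = 596 to 580 would be 0.501 to 0.515% instead of 0.498%. An Arm A or B participant given one placebo injection in error, with no second injection, is a remote case.

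**Conclusion.** A minor point that holds for first-injection tables only. Unless the shells say otherwise, the first-injection Total pools Arms A, B and C, with about 200 of about 600 having received saline. Its expected difference from Placebo is then two thirds of the A+B difference. This rests on equal arms and a common saline rate in Arms C and D. The size in percentage points rests on assumed saline rates and small Phase 1 groups.

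The arm columns are not affected. Nor are the any-vaccination and overall stages, apart from participants who received only placebo. The documents do not support a claim that the primary safety assessment as a whole is diluted.

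**What to change.** Amend SAP 6.1, and refer to it from 6.2.4, 6.3.1 and 6.3.1.5:

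1. In first-injection tables of solicited reactions, unsolicited adverse events and antipyretic or analgesic use, define mRNA-1893 Total as participants in the analysis set who received mRNA-1893 at that injection (Arms A+B, about 400). Alternatively, omit Total from those tables.
2. Label Arm C's Day 1 column as a placebo injection.
3. State that first and second vaccination mean injection order.

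Optionally, footnote the number of participants under Single Dose who never received mRNA-1893.

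The cost is SAP wording, one derived flag and footnotes, with no new data. The drawback is that Total would have about 400 participants for the first injection and about 600 for the second, and in first-injection tables would no longer equal the sum of the columns shown. The two Total columns would not be directly comparable, and a footnote should say so. Omitting Total from first-injection tables avoids this.

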5. STUDY POPULATION

The study will enroll approximately 800 adult participants aged 18 through 65 years at baseline, including approximately 400 flavivirus-seropositive participants and 400 flavivirus-seronegative participants, who will receive mRNA-1893 or placebo.

A dengue rapid point-of-care test initially used to stratify study participants has been discontinued. After this protocol amendment, all participants will be stratified based on geographic region, assuming most of the baseline seronegatives will come from continental US sites and the baseline seropositives from Puerto Rico. The confirmation will be done based on flavivirus serology testing (dengue immunoglobulin G [IgG] and immunoglobulin M [IgM], West Nile IgG and IgM) performed on a blood sample collected prior to administration of the first vaccination with a goal of an approximately equal distribution of participants among seronegative and seropositive participants within each treatment group.

The planned participant distribution is presented by treatment arm in Table 7.

	·		
Investigational Product	Baseline Flavivirus-Seronegative Participants	Baseline Flavivirus-Seropositive Participants	Total
mRNA-1893 μg (Treatment Arm A)	100	100	200
mRNA-1893 μg (Treatment Arm B)	100	100	200
mRNA-1893 μg (Treatment Arm C)	100	100	200
Placebo (Treatment Arm D)	100	100	200
Total	400	400	800

Table 7: Participant Distribution by Treatment Arm

Upon completion of all eligibility evaluations, the investigator will review the inclusion/exclusion criteria for each participant to determine if the participant is eligible for enrollment in the study. Participants who meet all eligibility criteria will be enrolled in the study.

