8.2. Clinical Laboratory Assessments

8.2.1. Baseline and Safety Laboratory Assessments

There are no screening criteria based on the flavivirus serostatus, meaning all participants are enrolled regardless of serostatus. However, this baseline flavivirus status will be confirmed by serology testings (dengue IgG and IgM, West Nile IgG and IgM) performed on a blood sample collected prior to administration of the first vaccination in order to eventually ensure that an approximate equal distribution of participants among subgroups is respected for the statistical analysis.

A point-of-care urine pregnancy test will be performed at the Eligibility Visit and before each IP injection (or at any time at the discretion of the investigator) for all female participants of childbearing potential.

The FSH level may be measured at the discretion of the investigator to confirm menopausal status.

There are no screening safety laboratory tests at the time of the eligibility evaluation of the participant. However, additional tests may be performed for safety reasons at any time during the study if determined necessary by the investigator or required by local regulations. Specifically, if the participant presents with signs or symptoms evoking a flavivirus infection, standard-of-care tests and treatment will apply, and results will be reported in the source documents and in the AE section of the eCRF.

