All analyses and data summaries/displays will be provided by flavivirus serostatus (flavivirus-seropositive, flavivirus-seronegative, and/or overall) unless otherwise specified,

please also refer to Section 6.5 Planned Analyses. Baseline flavivirus status is determined by serology testing.

A participant is baseline seronegative if at least three baseline serology testings (dengue IgG, dengue IgM, West Nile IgG and West Nile IgM) are negative, and none of the serology testings is positive. If at least one of the baseline serology testings is positive, the participant is baseline seropositive. If two or more of the serology testings are "missing" or "unknown", and none of the serology testings is positive, the baseline serostatus will be "unknown" or "missing". A single testing result of "equivocal" is considered as "unknown", regardless of the numeric values.

All analyses will be conducted using SAS Version 9.4 or higher.

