6.4.2. Primary Analysis of Antibody-Mediated Immunogenicity Endpoints

For each group, the following evaluations will be performed at Day 57, or at each time point at which blood samples are collected for antibody-mediated immunogenicity (unless otherwise specified):

 GMT of ZIKV-specific nAbs, in all participants, in initially flavivirus-seronegative, and in initially flavivirus seropositive- participants, as measured by PRNT, will be provided at Day 57 with corresponding 95% CI. The 95% CIs will be calculated based on the t-distribution of the log-transformed values then back transformed to

- the original scale for presentation. The following descriptive statistics will also be provided at Day 57: the number of subjects (n), median, minimum and maximum.
- Proportion of participants with seroconversion in ZIKV-specific nAbs from Day 1 to Day 57, as measured by PRNT will be tabulated with 2-sided 95% Clopper-Pearson CIs. The difference of the seroconversion rates between each mRNA-1893 group and placebo group will be provided with 2-sided 95% CIs using the Miettinen-Nurminen method.
- For ZIKV-specific nAb titers, the GMT at Day 57 for each vaccination group, and the ratio of GMT of mRNA-1893 μg (2-dose), mRNA-1893 μg (2-dose), mRNA-1893 μg (single-dose) vs. Placebo respectively, will be estimated based on an analysis of covariance (ANCOVA) model that will be carried out for flavivirus-seropositive groups and flavivirus-seronegative groups separately using the PP Set. The dependent variable will be the nAb at Day 57 with the vaccination group as a factor and the baseline values as covariate (if applicable, ie, for flavivirus-seropositive groups only). The GMT and corresponding 95% CI for each vaccination group, and the ratio of GMT of mRNA-1893 μg (2-dose), mRNA-1893 μg (single-dose) vs. Placebo respectively, together with corresponding 95% CI will be provided.

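### SAP 6.1 lets IgM negatives stand in for a missing or equivocal IgG, and no required analysis checks the seronegative stratum against the Day 1 ZIKV titre

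*SAP*

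**What the plan says.** Protocol 8.2.1 says that "this baseline flavivirus status will be confirmed by serology testings (dengue IgG and IgM, West Nile IgG and IgM"), on a sample taken before the first injection. Protocol 5 names the same four tests. No ZIKV assay is among them.

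SAP 6.1 turns the four results into a status:

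- Seronegative: "A participant is baseline seronegative if at least three baseline serology testings" (the same four) are negative, with none positive.
- Seropositive: any one of the four positive.
- Unknown or missing: "If two or more of the serology testings are 'missing' or 'unknown', and none of the serology testings is positive".
- Equivocal: "A single testing result of 'equivocal' is considered as 'unknown', regardless of the numeric values".

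The status is then used in the primary analysis. SAP 3.1 lists the Day 57 PRNT GMT in seronegative participants within the primary endpoint. SAP 6.4.2 fits the ANCOVA separately by serostatus, with vaccination group as a factor and "the baseline values as covariate (if applicable, ie, for flavivirus-seropositive groups only"). SAP 3.2 defines seroresponse, reported in seronegatives, as a rise from below LLOQ to LLOQ or above.

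**The concern.** The rule counts negatives without asking which tests gave them. An unknown dengue IgG is covered by dengue IgM, West Nile IgG and West Nile IgM; an unknown West Nile IgG is covered in the same way. In each case two of the three negatives are IgM. IgM marks recent infection, and Protocol 8.3.2 itself uses an IgM assay to confirm symptomatic cases. It does not show that a participant was never infected.

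The rule also takes no account of the Day 1 ZIKV titre, for which Protocol 4.1.2 schedules a sample from every participant. Two parts of the SAP nevertheless treat the seronegative stratum as free of baseline ZIKV antibody: the ANCOVA drops the baseline covariate there, and seroresponse can be met only from below LLOQ.

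At stake is the meaning of the seronegative results. Protocol 4.3 expects responses to differ by serostatus, Protocol 4.4 justifies the single-dose arm partly by populations with pre-existing immunity, and SAP 6.6 makes the Day 57 analysis the basis for moving to Phase 3. Previously exposed participants in the seronegative stratum would blur that contrast.

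**Working it through.** **1. The rule, enumerated.** Give each of the four tests one of three values: positive, negative or unknown (missing or equivocal). That makes 3^4 = 81 patterns. Applying SAP 6.1:

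- At least one positive: 81 − 2^4 = 65, seropositive.
- No positive and at least three negative: 5, seronegative.
- No positive and two or more unknown: 16 − 5 = 11, unknown or missing.

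The 5 seronegative patterns are all four negative, plus one for each single unknown test. One of the five has dengue IgG unknown and another has West Nile IgG unknown. If both IgG results must also be negative, those two move: 3 seronegative, 65 seropositive, 13 unknown. These are counts of patterns, not of participants.

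**2. Effect on GMT and ratio.** The documents give no figure to reproduce, so this is an illustration on assumed inputs. Let f be the misclassified share of a seronegative cell, the same in each arm. Let gP and gV be the log10 differences in Day 57 titre between misclassified and truly seronegative participants, in placebo and in vaccine. The mean log10 titre shifts by f × g in each arm, so:

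- placebo GMT is multiplied by 10^(f × gP);
- vaccine/placebo ratio is multiplied by 10^(−f × (gP − gV)).

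With no covariate, an ANCOVA on log titres returns these arm means, so the same factors apply to the modelled ratio.

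| f | gP | gV | Placebo GMT × | Ratio × |
|---|---|---|---|---|
| 1% | 1 | 0 | 1.02 | 0.98 |
| 5% | 1 | 0 | 1.12 | 0.89 |
| 5% | 1 | 0.5 | 1.12 | 0.94 |
| 5% | 1 | 1 | 1.12 | 1.00 |
| 10% | 1 | 0 | 1.26 | 0.79 |
| 10% | 1 | 0.5 | 1.26 | 0.89 |
| 10% | 2 | 0 | 1.58 | 0.63 |

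The ratio falls by the full placebo factor only when gV = 0. If gV exceeded gP, the ratio would rise.

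**3. Seroresponse.** A participant with a Day 1 titre at or above LLOQ can never be a seroresponder. Under the general denominator rule in SAP 6.1 that participant still counts. If a share h of the cell is in this position, seroresponse cannot exceed 1 − h: for example 95% at h = 5%.

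**4. Chance imbalance.** Suppose each of two arms of 100 seronegatives has an independent 5% misclassification rate. The simulated chance that they differ by 5 or more such participants is about 14%. It is about 2% at a 2% rate and about 29% at a 10% rate. The seronegative ANCOVA has no baseline term to adjust for it.

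**5. Whether another step removes these participants.** The Per-Protocol Set (SAP 5.5) excludes for dosing and sampling windows and for major deviations, not for serology. The sensitivity analysis in SAP 6.4.6 is optional and uses status from serology testing, which is already the main definition.

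**The case against.** The case for leaving the rule alone has substance.

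- **Frequency is unknown and may be small.** Protocol Table 9 plans one baseline collection for all four tests, so a lost sample would remove all four and already gives unknown status. What remains is an isolated assay failure or an equivocal IgG, and an equivocal result does not prove past infection.
- **Arms are balanced in expectation.** Status comes from a sample drawn before injection, so randomisation is not broken.
- **There is partial protection.** Primary seroconversion requires a 4-fold rise when a titre already exists. GMFR is measured within participants. Day 1 PRNT summaries in seronegatives will show baseline titres. The Day 57 GMT in all participants does not depend on serostatus.
- **The scale is modest.** There is no hypothesis test, and Protocol 9.2 speaks of detecting differences of 4-fold or more.
- **The dengue and West Nile panel is the protocol's choice.** Protocol 9.4.3 and 9.4.4 define status that way. Protocol 2.3.2 notes dengue–ZIKV cross-reactivity, so dengue testing may catch some past Zika exposure.

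All of this stands and limits the point. It does not close the gap: no test has to be an IgG for a participant's status to rest on it, and the protections describe baseline titres without providing an estimate free of them.

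Two stronger readings are tempting. A reader might infer that raising the placebo GMT lowers the vaccine/placebo ratio by the same factor. That assumes misclassified vaccinees have no titre gap, which nothing in the documents supports and which sits badly with any recall response. A reader might also infer that the missing Zika test is an SAP error and that the primary strata should be redefined by Day 1 PRNT. The SAP follows the protocol here, and such a redefinition would depart from it.

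**Conclusion.** The point holds in limited form. As written, SAP 6.1 can class a participant as seronegative with a missing or equivocal dengue IgG or West Nile IgG. It also keeps participants with a quantifiable Day 1 ZIKV titre in a stratum whose ANCOVA and seroresponse definition presuppose that there is none. Both statements follow from the text alone.

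The size is not known. The documents give no rate of isolated missing or equivocal IgG, no share of seronegatives with a Day 1 titre at or above LLOQ, and no titre gap. On assumed values of f = 5%, gP = 1 and gV = 0 the ratio is multiplied by 0.89. It moves less if vaccinees share part of the gap and not at all if they share all of it. The documents therefore do not show that the seronegative result will be materially biased, or in which direction. They show an avoidable looseness in a primary stratum that is worth tightening because it is cheap to do so.

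**What to change.** 1. In SAP 6.1, keep the present conditions for seronegative and add that dengue IgG and West Nile IgG must both be available and negative. Send participants with a missing or equivocal IgG and no positive test to the serostatus-missing group that SAP 6.4 already reports.
2. Keep the protocol's dengue and West Nile definition for the primary strata.
3. In SAP 6.4.6, replace the optional analysis with a required one: repeat the seronegative GMT, GMT ratio and seroresponse analyses in participants with Day 1 ZIKV PRNT below LLOQ, excluding those with a missing Day 1 PRNT.
4. Record the changes in SAP Section 7, which now lists none.
5. If unblinded results already exist under the current rule, keep that rule and add the strict IgG definition as a required sensitivity analysis.

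The cost is one changed derivation, one extra set of outputs and a Section 7 entry, with no new sample. The seronegative cells, planned at about 100 per arm, become slightly smaller. Participants who move to the missing group leave the serostatus-specific ANCOVA but stay in the overall summaries.
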